#### **4.7.1.3. Patient Reported Outcome Variables**

##### **Charcot-Marie-Tooth Health Index (CMT-HI)**

- CMT-HI total score
- The 18 subscale scores of the CMT-HI
  - Mobility, Foot and ankle strength, Balance, Activities, Hand and finger function, Shoulder and arm function, Numbness, Pain, Fatigue, Sleep and daytime sleepiness, Emotions, Social Performance, Cognition, Heartburn, Constipation, Hearing, Breathing, and Ability to swallow

#### **4.7.1.4. Physician Reported Outcome Variables**

##### **Charcot-Marie-Tooth Examination Score – Version 2 (CMTES2)**

- This is the sum of the following items from the CMT neuropathy score instrument (Murphy et al., 2011): Sensory symptoms, Motor symptoms (legs), Motor symptoms (arms), Pinprick Sensibility, Vibration, Strength (legs), and Strength (arms)
  - Each individual item is assessed using a rating from 0 to 4 inclusive. The range of CMTES2 scores is from 0 to 28 inclusive.

#### **4.7.2. Analyses**

##### **4.7.2.1. Part 1**

Unless otherwise specified, no imputations for missing data will be performed for Part 1 data.

##### **Muscle Strength [Maximum voluntary isometric contraction {MVIC}]**

Individual MVIC data will be listed.

Descriptive statistics of the raw data as well as the absolute and percent change from baseline will be provided by side treated [left and right]. The average absolute and average percent change from baseline for the left and right sides will also be provided.

Least squares mean estimates of the effect of ACE-083 and corresponding 90% and 95% confidence intervals will be produced for the average percent change data (left and right sides) at 3-weeks post last dose [theoretically the Day 106 assessment] described above using an analysis of covariance (ANCOVA) with BASELINE, COHORT, BASELINE\*COHORT, and CMT-TYPE as covariates where:

- COHORT represents the dose level of ACE-083 administered to the muscle
- BASELINE represents the baseline value (average for the left and right sides)
- BASELINE\*COHORT represents the interaction of the baseline and cohort
- CMT-TYPE refers to the type of patient (e.g. CMT1 or CMTX)

Additional analyses may be performed as appropriate.

## **Motor Function Variables**

Individual motor function data will be listed.

For motor function test variables (e.g. cumulative distance at 6 minutes from the 6-minute walk test, time to complete 10-meter walk/run test, gait parameters, Berg Balance Scale), descriptive statistics of the raw data as well as absolute and percent change from baseline will be provided. With the exception of gait parameters, cumulative distances at 1 to 5 minutes inclusive, and the Berg Balance Scale, least squares mean estimates of the effect of ACE-083 and corresponding 90% and 95% confidence intervals will be produced for the percent change data (as well as absolute change data for 6MWD) at 3 weeks post last dose [theoretically the Day 106/End-of-Treatment assessment] described above using an ANCOVA with BASELINE, COHORT, BASELINE\*COHORT, and CMT-TYPE as covariates where BASELINE refers to the baseline motor function value and the other covariates are defined similarly as for the strength variables above.

Additional analyses may be performed as appropriate.

## **Patient Reported Outcome Variables**

Individual CMT-HI data will be listed.

For CMT-HI total score and subscale scores, descriptive statistics of the raw data as well as absolute change from baseline will be provided.

Least square mean estimates of the effect of ACE-083 and corresponding 90% and 95% confidence intervals will be produced for the absolute change data at 3 weeks post last dose [theoretically the Day 106/End-of-Treatment assessment] described above using an ANCOVA with BASELINE, COHORT, BASELINE\*COHORT, and CMT-TYPE as covariates where BASELINE refers to the baseline patient reported outcome variable (i.e. CMT-HI total score or CMT-HI subscale score) and the other covariates are defined similarly as for the strength variables above.

Additional analyses may be performed as appropriate.

## **Physician Reported Outcome Variables**

Individual data from the CMTES2 will be listed.

For CMTES2, descriptive statistics of the raw data as well as the absolute and percent change from baseline will be provided.

Least square mean estimates of the effect of ACE-083 and corresponding 90% and 95% confidence intervals will be produced for the absolute change data at 3 weeks post last dose [theoretically the Day 106/End-of-Treatment assessment] described above using an ANCOVA with BASELINE, COHORT, BASELINE\*COHORT, and CMT-TYPE as covariates where BASELINE represents the baseline CMTES2 and the other covariates are defined similarly as for the strength variables above.

Additional analyses may be performed as appropriate.

#### 4.7.2.2. Part 2

##### 4.7.2.2.1. Double-Blind Period

###### Muscle Strength (MVIC)

Individual MVIC data will be listed.

Descriptive statistics of the raw data as well as the absolute and percent change from baseline will be provided by side treated [left and right]. The average absolute and average percent change from baseline for the left and right sides will also be provided.

A plot of the mean ( $\pm$  SEM) of the average percent change from baseline for the left and right sides by scheduled day and treatment group will also be provided.

An ANCOVA model will be fitted in order to assess the effect of ACE-083 on the average percent change from baseline for the left and right side at Day 190 with the following covariates: TREATMENT, MRC-MMT DECIMAL SCORE, BASELINE, CMT-TYPE where:

- TREATMENT represents the treatment group (ACE-083 or placebo)
- MRC-MMT DECIMAL SCORE represents the conversion of the screening MRC-MMT grade to the decimal version as follows: 5 = 5.0, 5- = 4.67, 4+ = 4.33, 4 = 4.0, 4- = 3.67, 3+ = 3.33, 3 = 3.0, 3- = 2.67, 2+ = 2.33, 2 = 2.0, 2- = 1.67, 1+ = 1.33, 1=1.0
  - This quantity will be the average from the left and right sides and will be computed for each individual patient.
- BASELINE represents the baseline MVIC (average of left and right sides)
- CMT-TYPE refers to the type of CMT (e.g. CMT1 or CMTX)

The effect of ACE-083 versus placebo will be estimated using the ANCOVA model described above and tested using a 0.1 significance level (2-sided). The least-square mean estimate along with the corresponding 90% confidence interval will be provided. In addition, the 95% confidence interval will also be provided. A bar chart of the least squares mean  $\pm$  SEM of the percent change from baseline will be provided.

If the Day 190 MVIC assessment has no missing data, then the above ANCOVA model will be used for analysis. If missing data is present, a standard multiple imputation with the above ANCOVA model will be used for analysis as described in Section 4.11.1.

A mixed model repeated measures (MMRM) analysis will be performed to assess the sensitivity to the ANCOVA analysis described above. An unstructured covariance structure will be used to model the within-patient covariance across visits. Other covariance structures will be considered if the unstructured covariance fails to converge. The covariates to be included consist of all of the covariates described above for the ANCOVA with the addition of the following additional covariates: VISIT where VISIT represents the scheduled visit day post first dose of MRI assessment and TREATMENT\*VISIT.

Similar to what was described for the ANCOVA analysis above, if missing data is present, a standard multiple imputation with the above MMRM model will be used for analysis as described in [Section 4.11.1](#).

The findings from the ANCOVA model described above will be considered primary.

Additional analyses may be performed as appropriate.

### **MRC-MMT Decimal Score**

Descriptive statistics will be provided for raw and percent change from baseline for the MRC-MMT decimal score for ankle dorsiflexion for each side where the MRC-MMT decimal score represents the conversion of the MRC-MMT grade to the decimal version as follows: 5 = 5.0, 5- = 4.67, 4+ = 4.33, 4 = 4.0, 4- = 3.67, 3+ = 3.33, 3 = 3.0, 3- = 2.67, 2+ = 2.33, 2 = 2.0, 2- = 1.67, 1+ = 1.33, 1=1.0. The average percent change from baseline for the left and right sides will also be provided.

An ANCOVA model will be fitted in order to assess the effect of ACE-083 on the average Day 190 absolute change in the MRC-MMT decimal score for ankle dorsiflexion with placebo. The ANCOVA model will contain the following covariates: TREATMENT, BASELINE MRC-MMT DECIMAL SCORE, and CMT-TYPE where BASELINE MRC-MMT DECIMAL SCORE represents the MRC-MMT decimal score for ankle dorsiflexion (average of right and left sides) and the other covariates are defined similarly as described for MVIC. A bar chart of the least squares mean  $\pm$  SEM of the percent change from baseline will be provided.

No imputations will be performed for missing data.

Additional analyses may be performed as appropriate.

### **10-Meter Walk/Run Test**

Individual data will be listed.

Descriptive statistics of raw data as well as absolute and percent change from baseline will be provided by treatment group for each scheduled time. A plot of mean  $\pm$  SEM will also be provided for the percent change from baseline for each treatment group.

An ANCOVA model will also be fitted in order to assess the effect of ACE-083 on the Day 190 percent change in the time to complete the 10-meter walk/run test from baseline data. Covariates to be included in the model are TREATMENT, HEIGHT, CMT-TYPE and BASELINE where BASELINE represents the baseline time to complete the 10-meter walk/run, HEIGHT represents the height of the patient in centimeters, and each of the other covariates are defined similarly as what was described for MVIC.

The effect of ACE-083 on the Day 190 percent change in the time to complete the 10-meter walk/run test from baseline versus placebo will be estimated using the ANCOVA model described above and tested using a 0.1 significance level (2-sided). The least-square mean estimate along with the corresponding 90% confidence interval will be provided. In addition, the 95% confidence interval will also be provided as well as a bar chart of the least squares mean estimates ( $\pm$  SEM) for each of the treatment groups.

If the Day 190 10-meter walk/run test has no missing data, then the above ANCOVA model will be used for analysis. If missing data is present, a standard multiple imputation with the above ANCOVA model will be used for analysis as described in [Section 4.11.1](#)

A mixed model repeated measures (MMRM) analysis will be performed to assess the sensitivity to the ANCOVA analysis described above. An unstructured covariance structure will be used to model the within-patient covariance across visits. Other covariance structures will be considered if the unstructured covariance fails. The covariates to be included consist of all of the covariates described above for the ANCOVA with the addition of the following additional covariates: VISIT where VISIT represents the scheduled visit day post first dose of MRI assessment and TREATMENT\*VISIT.

Similar to what was described for the ANCOVA analysis above, if missing data is present, a standard multiple imputation with the above MMRM model will be used for analysis as described in Section 4.11.1.

The findings from the ANCOVA model described above will be considered primary.

The analyses described above will also be done for the absolute change from baseline.

The analyses described above will also be repeated for the Full Analysis Set.

Additional analyses may be performed as appropriate.

## 6-Minute Walk Test

Individual data will be listed.

Descriptive statistics of raw data as well as changes from baseline (absolute and percent change) will be provided by treatment group by scheduled time separately for cumulative distance recorded at 1 minute, 2 minutes, 3 minutes, 4 minutes, 5 minutes, and 6 minutes. A plot of mean  $\pm$  SEM for the cumulative distance recorded at 6 minutes will also be provided for the percent change from baseline for each treatment group.

An ANCOVA model will be fitted in order to assess the effect of ACE-083 on the Day 190 percent change in the cumulative distance recorded at 6 minutes. Covariates to be included in the model are TREATMENT, HEIGHT, CMT-TYPE, and BASELINE where HEIGHT refers to the height of the patient (cm) and BASELINE represents the baseline distance walked in 6 minutes and each of the other covariates are defined the same as what was described for MVIC.

The effect of ACE-083 on the Day 190 percent change in the cumulative distance recorded at 6 minutes from baseline versus placebo will be estimated using the ANCOVA model described above and tested using a 0.1 significance level (2-sided). The least-square mean estimate along with the corresponding 90% confidence interval will be provided. In addition, the 95% confidence interval will also be provided as well as a bar chart of the least squares mean estimates ( $\pm$  SEM) for each of the treatment groups.

An ANCOVA model will also be fitted in order to assess the effect of ACE-083 on the Day 190 absolute change in the cumulative distance recorded at 6 minutes from baseline data. Covariates to be included in the model are TREATMENT, HEIGHT, CMT-TYPE, and BASELINE where HEIGHT refers to the height of the patient (cm) and BASELINE represents the baseline distance

walked in 6 minutes and each of the other covariates are defined the same as what was described for MVIC.

The effect of ACE-083 on the Day 190 absolute change in the cumulative distance recorded at 6 minutes from baseline versus placebo will be estimated using the ANCOVA model described above and tested using a 0.1 significance level (2-sided). The least-square mean estimate along with the corresponding 90% confidence interval will be provided. In addition, the 95% confidence interval will also be provided as well as a bar chart of the least squares mean estimates ( $\pm$  SEM) for each of the treatment groups.

If the Day 190 cumulative distance recorded at 6 minutes has no missing data, then the ANCOVA models described above will be used for analysis. If missing data is present, a standard multiple imputation with the above ANCOVA models will be used for analysis as described in [Section 4.11.1](#).

A mixed model repeated measures (MMRM) analysis will be performed to assess the sensitivity to the ANCOVA analyses described above. An unstructured covariance structure will be used to model the within-patient covariance across visits. Other covariance structures will be considered if the unstructured covariance fails. The covariates to be included consist of all of the covariates described above for the ANCOVA with the addition of the following additional covariates: VISIT where VISIT represents the scheduled visit day post first dose of MRI assessment and TREATMENT\*VISIT.

Similar to what was described for the ANCOVA analyses above, if missing data is present, a standard multiple imputation with the above MMRM model will be used for analysis as described in Section 4.11.1.

The findings from the ANCOVA model described above will be considered primary.

The analyses described above will also be done for the absolute change from baseline.

The analyses described above will also be repeated for the Full Analysis Set.

Additional analyses may be performed as appropriate.

### **Berg Balance Scale**

Individual data will be listed.

Descriptive statistics of raw data as well as changes from baseline (absolute and percent change) will be provided by treatment group and scheduled time.

An ANCOVA model will be fitted in order to assess the effect of ACE-083 on the Day 190 absolute change in the Berg Balance Score from baseline. Covariates to be included are TREATMENT, CMT-TYPE, and BASELINE where BASELINE refers to the baseline Berg Balance Score and the other covariates are defined similarly as for MVIC.

The effect of ACE-083 on the Day 190 absolute change in the Berg Balance Scale versus placebo will be estimated using the ANCOVA model described above and tested using a 0.1 significance level (2-sided). The least-square mean estimate along with the corresponding 90% confidence interval will be provided. In addition, the 95% confidence interval will also be provided as well as a bar chart of the least squares means estimates ( $\pm$  SEM) for each of the treatment groups.

If the Day 190 Berg balance assessment has no missing data, then the above ANCOVA model will be used for analysis. If missing data is present, a standard multiple imputation with the above ANCOVA model will be used for analysis as described in [Section 4.11.1](#).

The statistical analyses described above will be done on the Per Protocol Set and will be considered primary. The analyses described above will also be repeated for the Full Analysis Set.

Additional analyses may be performed as appropriate.

### **Falls**

Individual data on the number and type of falls recorded in 4-week time intervals along with details on the timing and classification of the individual falls recorded, type of assistance, and information related to input (whether the fall was recorded by device detection or recorded by the individual patient) will be provided in a listing.

The number of falls, as well as the number of patients who fell at least once occurring from Week 1 to Week 24 (6 months) will be summarized by treatment group. Summaries will be provided for the additional subintervals between Weeks 1 and 24 as outlined in [Section 4.7.1.2](#). A record of “Near-fall” will not be counted as a “Fall”.

The hazard ratio of recurring falls between ACE-083 and placebo between Weeks 1 and 24 will be estimated using the Andersen-Gill recurrent events model with the following covariates: TREATMENT, CMT-TYPE, and ankle dorsiflexion MRC-MMT decimal score where the covariates are defined similarly as what was described for MVIC. The point estimate, p-value and 90% confidence interval for the hazard ratio for TREATMENT will be provided.

Additional methods for the statistical analysis of the recurring event of falls may be considered and performed as appropriate (e.g. negative binomial regression with similar covariates as listed for the Andersen-Gill recurrent events model described above).

No imputations will be performed for missing data.

The statistical analyses described above will be done on the Per Protocol Set and will be considered primary. The analyses described above will also be repeated for the Full Analysis Set.

Additional analyses may be performed as appropriate.

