Planned Day(s)	-28 to -7	11	8 (±1d)	22 ¹ (±1d)	43 ¹ (±3d)	64 ¹ (±3d)	85 ¹ (±3d)	106 ¹ (±3d)	127 ¹ (±3d)	148 ¹ (±3d)	169 ¹ (±3d)	190 ¹ (±3d)	$\begin{array}{c}(211, 232, \\253, 274)^1\\(\pm 3d)\end{array}$	295 ¹ (±3d)	316 ¹ (±3d)	337 ¹ (±3d)	358 (±3d)	393 (±3d)
Informed consent	Х																	
Inclusion/exclusion criteria	X																	
Urine pregnancy test ³		Х		Х	Х	Х	Х	Х	Х	Х	Х	Х	Х	Х	Х	Х		
Medical history	Х	Х																
MMT assessment (MRC) ⁴	Х											Х		Х			Х	Х
Genetic testing ⁵	Х																	
Full physical examination ⁶	Х							Х				Х		Х			Х	Х
Limited physical examination ⁷		Х		Х		Х			Х	Х	Х		Х		Х	Х		
Injection site examination ⁸		Х	Х	Х	Х	Х	X	Х	Х	Х	Х	Х	Х	Х	Х	Х		
Vital signs ⁹	Х	Х	Х	Х	Х	Х	Х	Х	Х	Х	Х	Х	Х	Х	Х	Х	Х	
Hematology ¹⁰	Х	Х		Х	Х	Х	Х	Х		Х		Х	Х	Х		Х	Х	
Chemistry ¹⁰	X	Х		Х	Х	Х	Х	Х		Х		Х	X	Х		Х	Х	
Urinalysis ¹⁰	Х	Х			Х	Х	Х	Х		Х		Х	Х	Х		Х	Х	
Biomarkers ¹¹	Х	Х		Х	Х	Х	Х	Х		Х		Х	Х	Х		Х	Х	Х
Anti-drug antibody		Х	Х	Х	Х	Х	Х	Х		Х		Х	Х	Х		Х	Х	X ¹²
Serum PK ¹³		0, 1, 2, 4, 6 h	Х				0, 1, 2, 4, 6 h					Х		Х			Х	Х
ECG (12 lead)	Х	$4 h^{14}$					$4 h^{14}$											
Bilateral MRI ¹⁵		Х			Х			Х				Х		Х			Х	Х
Timed function tests ¹⁶	X	Х		Х	Х	Х	Х	Х		Х		Х	X	Х		Х	Х	Х
Balance and gait tests ¹⁷	Х	Х						Х				Х		Х			Х	Х
Strength tests ¹⁸	X	Х	Х	Х	Х	Х	Х	Х		Х		Х	Х	Х		Х	Х	Х
CMTES2 ¹⁹	X	Х						Х				Х		Х			Х	Х
CMT-HI ¹⁹	Х				Х			Х		Х		Х		Х			Х	Х

Table 6: Schedule of Events for Part 2: Randomized, Double-Blind, Placebo-Controlled with Open-Label Extension

09 January 2019

CMAP of tibialis anterior

Х

Х

Х

Clinical Study Protocol Study A083-03 Revision: 03

	Screening				Double	Blind, Pl	acebo-Cont	rolled					Open	-Label			ET ²	EOS ²³
Dose(s)		1		2	3	4	5	6	7	8	9	10	11, 12, 13, 14	15	16	17		
Planned Day(s)	-28 to -7	1^1	8 (±1d)	22 ¹ (±1d)	43 ¹ (±3d)	64 ¹ (±3d)	85 ¹ (±3d)	106 ¹ (±3d)	127 ¹ (±3d)	148 ¹ (±3d)	169 ¹ (±3d)	190^{1} (±3d)	$(211, 232, 253, 274)^1$ (±3d)	295 ¹ (±3d)	316 ¹ (±3d)	337 ¹ (±3d)	358 (±3d)	393 (±3d)
Monitoring of concomitant medications	Х	Х	Х	Х	Х	Х	Х	Х	Х	Х	Х	Х	Х	Х	Х	Х	Х	Х
Monitoring of adverse events		Х	Х	Х	Х	Х	Х	Х	Х	Х	Х	Х	Х	Х	Х	Х	Х	Х
Randomization ²⁰		Х																
Distribution of PAMSys TM Device ²¹	Х																	
Study drug administration ²²		Х		Х	Х	Х	Х	Х	Х	Х	Х	Х	Х	Х	Х	Х		

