¹⁵ MRI assessments should be completed within 5 days prior to the scheduled dose administration, with the exception of the Day 1 MRI which may be completed within 14 days prior to Day 1 visit. MRI assessments during the follow-up period (Day 358/ET and Day 393/EOS) have a ± 5 day window.

¹⁶ 10-meter walk/run, 6-minute walk, 100-meter timed test (Part 2, open-label only; starting at the Dose 10 visit and continuing through to the EOS visit at all timepoints noted). Tests may be performed within 3 days prior to Day 1 visit.

¹⁷ Gait parameters, Berg balance scale. Tests may be performed within 3 days prior to Day 1 visit.

¹⁸ Maximum voluntary isometric contraction testing will be conducted using a handheld dynamometer. Both sides will be tested (right and left).

¹⁹ CMTES2 to be assessed by investigator; CMT-HI to be completed by patient

²⁰ Randomization should occur within 24 hours prior to Day 1 dose.

²¹ PamSysTM device is a physical activity monitoring system that will be worn by the patient for the duration of the study.

²² Study drug administration should occur within 21 days (\pm 3 days) of the previous dose.

²³ If subjects enroll directly into a separate extension study and will receive additional treatment with ACE-083, they do not need to complete the EOS visit. For these subjects, their final Study Visit in this protocol will be the ET visit.

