### 4.4.2. Baseline Characteristics

Baseline characteristics of the patient population consist of selected items from the CMT disease history, MRI, MRC-MMT, and functional test data. Such data includes the following:

- Age at onset of symptoms (years)
- Age at diagnosis (years)
- Duration since onset of symptoms (years)
  - Duration since onset of symptoms = Age (years) – Age at onset of symptoms (years)
- Duration since diagnosis (years)
  - Duration since diagnosis = Age (years) – Age at diagnosis (years)
- Total muscle volume (mm^3)
  - See [Section 4.8.1](#) for definition.
- Total muscle mass (g)
  - See [Section 4.8.1](#) for definition.
- Calculated contractile muscle volume (mm^3)
  - See [Section 4.8.1](#) for definition.
- Calculated contractile muscle mass (g)
  - See [Section 4.8.1](#) for definition.
- Fat fraction (%)
- 6-minute walk distance (m)
- Time to complete 10 meter walk/run (s)

- Number and percent of patients belonging to specified CMT Type (i.e., CMT1, CMTX)
- Number and percent of CMT1 patients belonging to specified CMT1 subtype/gene mutation (e.g., CMT1A, CMT1B)
- Number and percent of CMTX patients belonging to specified CMTX subtype/gene mutation (e.g., CMTX1)
- Number and percent of patients belonging to specific forms of CMT (e.g., demyelinating, axonal, mixed)
- Number and percent of patients with first degree relatives with CMT
- Number and percent of patients who have fallen to the ground in the past 6 months
- Number and percent of patients who have had past history of fractures
- Number and percent of patients who have had past surgery for CMT
- Number and percent of patients who wears any lower limb orthotics/braces
- Number and percent of patients who uses assistive devices
- Number and percent of patients who have a regular (at least once a week) exercise program
  - For those who have a regular exercise program, the type (aerobic, resistance training, or both) and frequency of exercise program (1-2, 3-4, or 5+ times per week) will also be summarized.
- Number and percent of patients who have known nerve conduction velocity
  - For those who have a known nerve conduction velocity, the category ( $< 38$  m/s,  $\geq 38$ ) will also be summarized.
- Number and percent of patients with MRC-MMT grades belonging to the following categories: [3 to 4-], [4 to 4+], [5- to 5]

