### **Activity Level (Part 2 double-blind and open-label)**

Activity level is defined as the average number of steps per day as measured by the PAMSys™ device over the patient's study participation, adjusted for overall compliance in using the device to record such activity.

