### **Falls**

The hazard ratio of recurring falls between ACE-083 and placebo during the entire 12 months (excluding the screening interval) will be estimated using the Andersen-Gill recurrent events model with the following covariates: SEQUENCE, CMT-TYPE, PERIOD, and ankle dorsiflexion MRC-MMT decimal score where SEQUENCE refers to the treatment sequence from double-blind to open-label (ACE-083  $\rightarrow$  ACE-083 or Placebo  $\rightarrow$  ACE-083), and PERIOD

refers to the period of time of observation (“Double-blind”, “Open-label”). The “Double-Blind” period covers Weeks 1 to 24 and the “Open-label” period covers Weeks 25 to 48. The point estimate, p-value and 90% confidence interval for the hazard ratio for SEQUENCE will be provided.

Additional methods for the statistical analysis of the recurring event of falls may be considered and performed as appropriate (e.g. negative binomial regression with similar covariates as listed for the Andersen-Gill recurrent events model described above).

No multiple imputations will be performed for missing data.

The statistical analyses described above will be done on the Per Protocol Set and will be considered primary. The analyses described above will also be repeated for the Full Analysis Set.

Additional analyses may be performed as appropriate.

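### The falls models leave out pre-treatment falls, although six-month fall history is collected and every other modelled double-blind efficacy endpoint adjusts for its own baseline

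*SAP*

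**What the plan says.** SAP 4.7.2.2.1 (Falls) states that the hazard ratio for recurrent falls "between Weeks 1 and 24 will be estimated using the Andersen-Gill recurrent events model with the following covariates", and lists "TREATMENT, CMT-TYPE, and ankle dorsiflexion MRC-MMT decimal score where the covariates are defined similarly" to those for MVIC. It adds: "The point estimate, p-value and 90% confidence interval for the hazard ratio for TREATMENT will be provided". A negative binomial model with similar covariates is optional. Missing falls data are not imputed.

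SAP 4.7.2.2.3 (Falls) extends the model to falls "during the entire 12 months (excluding the screening interval"), with treatment sequence, CMT type, period and dorsiflexion score as covariates.

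Neither model has a term for falls before the first dose. The responder criterion for falls in SAP 4.7.2.3 compares Weeks 13 to 24 with Weeks 1 to 12, so it has no pre-treatment reference either.

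SAP 4.4.2 lists among the baseline characteristics: "Number and percent of patients who have fallen to the ground in the past 6 months".

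On the device, the Part 2 schedule in Protocol Appendix 1 marks "Distribution of PAMSys" at Screening, and a footnote says the "device is a physical activity monitoring system that will be worn by the patient for the duration of the study". SAP 4.7.1.2 defines activity level as average daily steps, "adjusted for overall compliance in using the device to record such activity". No such adjustment is stated for falls. The falls listing separates falls detected by the device from falls entered by the patient, and both kinds are recorded.

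**The concern.** A patient's earlier falls are the natural baseline for later falls. The SAP follows the baseline principle elsewhere in the double-blind period: MVIC, MRC-MMT score, 10-metre walk/run, 6-minute walk, Berg, CMT-HI, CMTES2 and mid-swing foot angle are each modelled with their own baseline value. Falls are the one exception, and no reason is given.

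What is at stake is precision. The trial is small, fall counts usually vary widely between patients, and the SAP plans a p-value and interval for the falls hazard ratio, a 12-month model and subgroup analyses of fall risk. A prognostic covariate already in the database would be left unused. If it is added after unblinding, the choice carries less weight than one made in advance.

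Device wear is a secondary question. The SAP allows for incomplete wear when counting steps but does not say how unworn time is treated when counting falls.

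**Working it through.** **The plan's own figure.** No fall rate, dispersion, event count or power is given for falls. The Part 2 sample size rests on muscle volume: a difference of 10, SD 10, two-sided 0.10. A t-test with 18 per arm has power 0.902 (0.887 with 17), and 36/0.90 = 40 randomized, so that figure reproduces. The falls check uses 18 per arm.

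**Value of fall history.** Assumptions, because the documents give none: 1, 3 or 6 falls per patient per 24 weeks; gamma-Poisson counts with shape 0.5, 1 or 2; hazard ratio 1 or 0.5. The model is a Poisson rate model (Andersen-Gill with a constant baseline hazard) with sandwich standard errors, and each scenario has 1,500 runs. SD of the log hazard ratio when the true ratio is 1:

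| Falls per 24 weeks | Shape | No history | Yes/no history | Change |
|---|---|---|---|---|
| 1 | 0.5 | 0.638 | 0.567 | -11% |
| 1 | 1 | 0.520 | 0.493 | -5% |
| 1 | 2 | 0.427 | 0.420 | -2% |
| 3 | 0.5 | 0.530 | 0.473 | -11% |
| 3 | 1 | 0.410 | 0.382 | -7% |
| 3 | 2 | 0.318 | 0.309 | -3% |
| 6 | 0.5 | 0.504 | 0.462 | -8% |
| 6 | 1 | 0.368 | 0.345 | -6% |
| 6 | 2 | 0.274 | 0.264 | -4% |

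In the middle scenario (3 falls, shape 1) with a true ratio of 0.5, the rejection rate rises from 0.52 to 0.57. Under no effect the same tests reject in 0.13 and 0.14 of runs, so the power gain is approximate.

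**Instability.** With rate r and shape k, the share of patients with no fall in a window of that length is (1 + r/k)^(-k). For r = 6 and k = 2 this is (1 + 3)^(-2) = 0.0625, or about 2 of 36 patients. In that setting up to 434 of 1,500 fits with the yes/no term (29%) were unusable.

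**Device wear.** Let w be the share of time worn (wA for ACE-083, wP for placebo) and s the share of off-wear falls that patients enter themselves. With no true effect:

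- Planned analysis: apparent ratio = [wA + (1 - wA)s] / [wP + (1 - wP)s].
- All falls with worn time as exposure: the same ratio multiplied by wP/wA.

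For wA = 0.80 and wP = 0.90:

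| s | Planned analysis | All falls, worn time as exposure |
|---|---|---|
| 0 | 0.80/0.90 = 0.89 | 0.89 × 1.125 = 1.00 |
| 0.5 | 0.90/0.95 = 0.95 | 0.947 × 1.125 = 1.07 |
| 1 | 1.00/1.00 = 1.00 | 1.00 × 1.125 = 1.125 |

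Where wear varies between patients but is unrelated to arm, the simulated mean log ratio stays near 0, and an offset for wear lowers the SD by at most about 4% (0.448 to 0.428).

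**The case against.** Falls are an exploratory endpoint for which the trial was not sized. Leaving out a prognostic covariate does not invalidate a randomized comparison, and the model already adjusts for dorsiflexion strength and CMT type. The simulation contained neither of those covariates, so the gain will be smaller if they already explain part of the variation in falls. All of this stands, and it makes the point a refinement. It does not explain why falls alone lack a baseline term.

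A reader might infer three stronger things, which the documents do not support.

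- **That device wear biases the falls hazard ratio.** This needs wear to differ by arm and off-wear falls to go unrecorded. Treatment is blinded, nothing suggests unequal wear, and patients can enter falls themselves. A chance difference is possible. With 18 per arm and an assumed SD of 0.2 in share of time worn, the SD of the arm difference is 0.2 × √(2/18) = 0.067, so a gap above 10 points has probability 0.13 (0.32 if the SD is 0.3). Those SDs are assumptions.
- **That worn days should be the exposure for all falls, as for steps.** Steps have no documented patient-entry route, but falls do. Off-wear falls would then be counted against a denominator that excludes off-wear time, which can turn a ratio of 1.00 into 1.125. The SAP also mentions only overall compliance, not dated worn days.
- **That a screening-period fall count is ready to use.** The fall variables in SAP 4.7.1.2 begin at Week 1, and no screening count is defined. Its existence is only implied by the exclusion of the screening interval. Screening runs from Day -28 to Day -7, so device time before dosing could be about 1 to 4 weeks. In 2,000 runs per scenario, a 21-day count changed the SD by anything from +1% to -30%.

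**Conclusion.** The point holds as a low-severity improvement. Both Andersen-Gill models omit pre-treatment falls although a six-month yes/no history is collected. Using it should lower the SD of the log hazard ratio by about 2% to 11%.

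That range rests on assumed rates of 1 to 6 falls per 24 weeks and assumed dispersion, and on past and future falls reflecting the same patient-level tendency. It applies to the yes/no item only, because the documents do not show that a six-month count was recorded.

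On wear, the documents support a gap in reporting and sensitivity analysis, not a finding of bias. The 0.89 at 80% versus 90% wear is the extreme case in which every off-wear fall is lost.

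**What to change.** Before unblinding, amend SAP 4.7.2.2.1 and 4.7.2.2.3 (Falls) as follows.

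1. Add a yes/no covariate for a fall in the past six months to both Andersen-Gill models and to the optional negative binomial model.
2. State a rule, applied to blinded pooled data, for dropping the term when nearly all patients are in one category. One option is fewer than 4 patients in the smaller category, which echoes the minimum size in SAP 4.9.
3. Keep the main analysis on all recorded falls and do not make worn time its exposure. Report device wear by arm.
4. Add a sensitivity analysis restricted to device-detected falls, with log worn time as the offset. A per-patient compliance figure is enough for this.

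The cost is SAP wording, one extra model term that can be unstable when almost everyone has fallen, one wear table and one sensitivity model. No new data collection appears necessary, provided device compliance is held per patient, as the step-count adjustment implies.
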